#### **9.4.2 Primary endpoint(s)**

The BOR is the best overall response observed from the date of first IMP until disease progression, death, cut-off date or initiation of post-treatment anti-cancer therapy, whichever occurs first. The BOR will be summarized with descriptive statistics. The ORR is the primary endpoint defined as the percentage of participants from the analysis population with BOR is either CR or PR, assessed per Investigator. The ORR and the corresponding 90% confidence intervals calculated from Clopper-Pearson exact method will be also presented. All objective responses need to be confirmed by a subsequent assessment performed at least 4 weeks apart from the initial response observation.

#### **9.4.3 Secondary endpoint(s)**

The secondary endpoints include efficacy (TTR, DOR, CBR, PFS), safety, immunogenicity, and PK.

##### **9.4.3.1 Time to response**

Time to response will be defined as the time from the first administration of IMP to the first tumor assessment at which the overall response was recorded as PR or CR that is subsequently confirmed.

Time to response will be descriptively summarized on the subgroup of participants who have achieved confirmed objective response in the efficacy population.

##### **9.4.3.2 Duration of response**

The DoR will only be summarized on the subgroup of participants who have achieved confirmed objective response in the efficacy population.

The DoR will be defined as the time from the date of first tumor assessment at which the overall response was recorded as PR or CR that is subsequently confirmed to the date of first documentation of objective PD before the initiation of any post-treatment anti-cancer therapy or death due to any cause, whichever occurs first.

Duration of response will be summarized with descriptive statistics using Kaplan-Meier methods. The median DoR and associated 90% CI will be provided.

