### 3 OBJECTIVES AND ENDPOINTS

**Table 2 - Objectives and endpoints**

| Objectives   | Endpoints  |
|--|--|
| Primary   |  |
| 
 
To determine the antitumor activity of SAR444245 in combination with other anti-cancer therapies in patients with HNSCC
 
                            | 
 
Objective response rate (ORR) defined as proportion of participants who have a confirmed complete response (CR) or partial response (PR) determined by Investigator per Response Evaluation Criteria in Solid Tumors (RECIST) 1.1 (1)
 
  |
| Secondary   |  |
| 
 
To assess the safety profile of SAR444245 when combined with other anti-cancer therapies
 
To assess other indicators of antitumor activity
 
 | 
 
Incidence of TEAEs, SAEs, laboratory abnormalities according to National Cancer Institute Common Terminology Criteria for Adverse Events (NCI CTCAE) V 5.0 and American Society for Transplantation and Cellular Therapy (ASTCT) consensus grading (2)
 
Time to response (TTR) defined as the time from the first administration of investigational medicinal product (IMP) to the first tumor assessment at which the overall response was recorded as PR or CR that is subsequently confirmed and determined by Investigator per RECIST 1.1
 
Duration of Response (DoR), defined as the time from first tumor assessment at which the overall response was recorded as PR or CR that is subsequently confirmed until documented progressive disease (PD) determined by Investigator per RECIST 1.1 or death from any cause, whichever occurs first
 
Clinical benefit rate (CBR) including confirmed CR or PR at any time or stable disease (SD) of at least 6 months (determined by investigator per RECIST 1.1)
 
Progression free survival (PFS), defined as the time from the date of first IMP administration to the date of first documented disease progression determined by Investigator as per RECIST 1.1, or death due to any cause, whichever occurs first
 
 |
| 
 
To assess the concentrations of SAR444245
 
To assess the immunogenicity of SAR444245
 
   | 
 
Plasma concentrations of SAR444245
 
Incidence of anti-drug antibodies (ADAs) against SAR444245
 
   |

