### **8.1.1 Assessment of objective response using the most appropriate modality according to the nature of the measurable lesion(s)**

For participants with disease that is measured radiologically according to RECIST 1.1 criteria ([Section 10.9](#)) a CT or magnetic resonance imaging (MRI) for tumor assessment will be performed as detailed in [Section 1.3](#). The choice of whether the imaging is by CT (preferred) or MRI is an Investigator decision. Once the choice of CT scan or MRI has been made, the same imaging technique should be used in a participant throughout the trial.

Baseline imaging should include all known target lesions. Baseline scans must evaluate extent of disease, including imaging of head, chest, abdomen (pelvis is optional) and any other locations with suspicion or evidence of disease involvement. This may be accomplished with CT chest, abdomen, and pelvis with contrast, or CT chest with contrast and MRI abdomen/pelvis with gadolinium.

The initial CT/MRI tumor imaging will be performed within 28 days prior to C1D1. Scans performed as part of routine clinical management are acceptable for use as the screening scan if they are of diagnostic quality and performed within 28 days prior to the date of enrollment. On-study imaging will be performed every 9 weeks ( $63 \pm 7$  days) after the date of first IMP and if clinically indicated. Imaging studies should follow calendar days and should not be adjusted for delays in cycle starts or extension. After Week 45 tumor imaging should be performed every 12 weeks ( $84 \pm 7$  days). Per the primary tumor assessment criteria, after the first documentation of response or the first documentation of progression (if the participant is clinically stable), confirmatory imaging may be performed no fewer than 28 days later. Alternately, the scan performed at the next scheduled time point (eg, every  $63 \pm 7$  days) may be used as confirmation. Tumor assessment is not needed for participants who start another anticancer therapy.

At a minimum, all radiologically measurable target lesions (RECIST 1.1) should be imaged at each response assessment. The same radiologic imaging modality should be used at each response assessment.

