#### **9.4.3.4 Progression-free survival**

Progression-free survival is defined as the time from the date of first IMP to the date of the first documentation of objective progressive disease when relevant or death due to any cause, whichever occurs first.

The analysis of PFS will be based on the following censoring rules:

- If progression or death is not observed before the cohort cut-off date and prior to the initiation of a further anticancer therapy, then PFS will be censored at the date of the last valid tumor assessment performed before the cohort cut-off date or date of initiation of a further anticancer therapy, whichever is earlier.
- A participant without event (death or disease progression) and without any valid post-baseline tumor assessment will be censored at the day of first IMP (Day 1).

Progression-free survival will be summarized on the efficacy population using Kaplan-Meier methods. The median PFS times and associated 90% CI will be provided.

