**10.10 APPENDIX 10:**

**10.10.1 Response and stable disease duration (RECIST 1.1 [REDACTED])**

Response duration will be measured from the time measurement criteria for CR/PR [REDACTED] (whichever is first recorded) are first met until the first date that recurrent or PD is objectively documented, taking as reference the smallest measurements recorded on study (including baseline).

Stable disease duration will be measured from the time of start of treatment until the criteria for progression are met, taking as reference the smallest sum on study (including baseline).

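### Duration of response ignores progression after a switch of therapy but counts death at any later time, which does not match the PFS and best-response rules

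*Protocol*

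**What the plan says.** Section 9.4.3.2 starts DoR at the first assessment showing a response that is later confirmed. It ends DoR at "first documentation of objective PD before the initiation of any post-treatment anti-cancer therapy or death due to any cause", taking the earlier of the two. On estimation it says "Duration of response will be summarized with descriptive statistics using Kaplan-Meier methods", with a median and 90% CI. It states no censoring rule.

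Section 9.4.3.4 defines PFS by progression or death and then adds censoring rules. The main one begins "If progression or death is not observed before the cohort cut-off date and prior to the initiation of a further anticancer therapy". In that case "PFS will be censored at the date of the last valid tumor assessment performed before the cohort cut-off date" or before the start of further therapy, whichever is earlier.

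Section 9.4.2 closes the window for best overall response at progression, death, cut-off or new anticancer therapy, whichever is first.

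Table 2 and the synopsis define DoR as running "until documented progressive disease (PD) determined by Investigator per RECIST 1.1 or death from any cause, whichever occurs first", with no condition on new therapy.

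Section 4.1 foresees participants who stop without progression, are imaged until they start another therapy, and then move to telephone survival follow-up. That follow-up runs until death, refusal or the final cohort cut-off, unless the sponsor cancels it sooner. Section 8.1.1 adds: "Tumor assessment is not needed for participants who start another anticancer therapy".

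**The concern.** DoR, PFS and best overall response describe the same disease course in the same participants, so they should treat a change of therapy in the same way. Here best overall response stops at the switch and PFS is censored before it. DoR passes through the switch, but for one of its two event types only.

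After a switch, scans are no longer required and progression would not count in any case. The only DoR event left is death, which may come many months into another treatment. That interval enters the DoR analysis as time in response to the study regimen, although no disease assessment is required during it.

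This is more than a censoring detail left open. The section states which events end a response, and that statement conflicts with the PFS rule.

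**Working it through.** The protocol gives no planned figure for DoR or PFS, so there is none to reproduce. The check applies the rules to one participant and then looks at the effect on the median.

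**One participant.** The weeks are assumed; the scans fit the nine-weekly schedule in Section 8.1.1. First confirmed response Week 9, last valid scan Week 27, new therapy without progression Week 30, death Week 80.

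| Rule | Calculation | Result |
|---|---|---|
| Time to response | first dose to Week 9 | 9 weeks |
| PFS, Section 9.4.3.4 | last valid scan before the switch | 27 weeks, censored |
| DoR, Section 9.4.3.2 as written | 80 - 9 | 71 weeks, event |
| DoR under the PFS rule | 27 - 9 | 18 weeks, censored |

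- Of the 71 weeks, 80 - 30 = 50 fall after the next therapy began.
- The DoR event time exceeds the censored PFS time by 71 - 27 = 44 weeks.
- Under a shared rule, DoR equals PFS minus time to response: 27 - 9 = 18.
- If progression were documented at Week 45 on the next therapy, Section 9.4.3.2 would still give 71 weeks. The Table 2 wording would give 45 - 9 = 36 weeks.

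**Effect on the median.** The documents give no switch rate, time to progression or survival after a switch, so these are assumptions. Two simulations of 200,000 responders per scenario compared Section 9.4.3.2 as written with censoring at the switch date.

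- *Exponential switch times:* 10% to 30% of responders switch before progression, median time from response to progression 6 to 12 months, median survival after the switch 10 to 13 months, follow-up cut at 36 months. The median DoR as written minus the median with censoring ranges from about -0.3 months (progression median 12, post-switch survival 10, 30% switching) to +0.6 months (6, 13, 30%).
- *Planned switches 2 to 8 months after response:* planned in 10% to 30%, of which 7% to 23% of all responders actually switch before progression. Median time to progression is 8 or 12 months, median survival after progression or switch 12 months, and follow-up ends 36 months from first dose. Median DoR is 8.1 to 8.4 months as written against 8.0 with censoring, or 12.0 against 12.0. DoR as written is longer than the PFS time in 6% to 20% of responders.

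The sign varies for a simple reason. After the switch, the rule as written replaces the risk of progression with the risk of death on the next therapy. If post-switch survival is longer than time to progression, the curve is pulled up; if shorter, it is pulled down; if the two are equal, it hardly moves.

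**Small numbers.** Table 5 includes 8 responders among 40 (20.0%). One such participant would then be 1/8 = 12.5% of the DoR sample and could set the tail of the curve.

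**The case against.** The strongest reply is that the comparison is uneven. The PFS definition sentence does not limit death either; the limit comes from the censoring rules below it. Section 9.4 calls itself a summary and leaves technical detail to the SAP, which may contain a matching DoR rule. This has force for the missing censoring rule, which alone would not be a finding. It does not remove the point: Section 9.4.3.2 writes a switch limit into its event definition, attaches it to progression and leaves death outside. A SAP that censored deaths after a switch would depart from that wording. The limit could be stretched to cover death, but the word order does not support this.

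A reader might infer that the worked case is a logical impossibility, since response cannot outlast progression-free time. The documents do not support that reading. A PFS time censored at 27 weeks is a lower bound, so an event at 71 weeks is an inconsistent treatment of the same person and not a contradiction between two observed durations. The date of death is also chosen; an earlier death narrows the gap.

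A reader might also infer that the rule would distort comparison with the pembrolizumab monotherapy DoR of 20.9 months against 4.5 in Substudy 01, Section 2.2.3.1. That section leads with overall survival, and the first-line trial's DoR censoring rule is not given. The historical benchmark in Section 4.2 concerns response rate.

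Finally, Table 2 and Section 10.10.1 should not be read as two further competing analysis rules. Table 2 is a summary and gives PFS no switch limit either. Section 10.10.1, which measures response "until the first date that recurrent or PD is objectively documented", is response-criteria text under a partly redacted heading.

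**Conclusion.** The point holds as an inconsistency in stated rules and is worth correcting, at moderate weight. For any responder who switches without progression and later dies within follow-up, Section 9.4.3.2 counts time on the next therapy as response, while PFS is censored before the switch and best overall response is closed at it. This follows from the text and needs no numerical assumption.

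The size does rest on assumptions. With 10% to 30% of responders switching before progression and the progression and survival medians above, the median DoR moves by about -0.3 to +0.6 months, in either direction. It would be wrong to infer a systematic inflation of the median. The consequence lies mainly in individual durations and the Kaplan-Meier tail. DoR is a secondary endpoint reported descriptively, no formal testing is planned, and no stated decision depends on it. How many later deaths are captured also depends on the sponsor continuing survival calls.

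**What to change.** State in Section 9.4.3.2 that DoR uses the same event and censoring rules as PFS: progression or death counts only if it precedes further anticancer therapy; otherwise DoR is censored at the last valid tumor assessment before further therapy or the cohort cut-off, whichever is earlier. Have Table 2 and the synopsis refer to that rule, and carry it into the SAP. If death after a switch is meant to count, say so explicitly and treat PFS the same way.

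The change is one sentence plus cross-references and needs no new data. It adds some censored observations to a small sample, and that censoring may be informative if participants switch because decline is expected. A sensitivity analysis counting progression and death after the switch, reported alongside, would show how much this matters. Its progression dates after the switch would be incomplete, because scans are no longer required then.

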##### **9.4.3.3 Clinical benefit rate**

The CBR will be defined as the proportion of participants with clinical benefit (confirmed CR or PR as BOR, or stable disease (SD) lasting at least 6 months). Specifically, participants will be considered as clinical benefit responders if they achieve a CR or PR as BOR, or have an overall

response recorded as SD at 6 months (ie, 26 weeks or later from first IMP intake, allowing for the  $\pm 7$  days visit window for tumor assessment scheduled at 27 weeks).

#### **9.4.3.4 Progression-free survival**

Progression-free survival is defined as the time from the date of first IMP to the date of the first documentation of objective progressive disease when relevant or death due to any cause, whichever occurs first.

The analysis of PFS will be based on the following censoring rules:

- If progression or death is not observed before the cohort cut-off date and prior to the initiation of a further anticancer therapy, then PFS will be censored at the date of the last valid tumor assessment performed before the cohort cut-off date or date of initiation of a further anticancer therapy, whichever is earlier.
- A participant without event (death or disease progression) and without any valid post-baseline tumor assessment will be censored at the day of first IMP (Day 1).

Progression-free survival will be summarized on the efficacy population using Kaplan-Meier methods. The median PFS times and associated 90% CI will be provided.

#### **9.4.3.5 Adverse events**

All AEs will be categorized according to NCI-CTCAE v 5.0 and classified by SOC and Preferred Term (PT) according to the latest available version of the Medical Dictionary for Regulatory Activities (MedDRA). Immune Cell-Associated Neurotoxicity Syndrome and CRS events will be graded using ASTCT Consensus Grading and will be summarized separately.

- Pre-treatment AEs are defined as any AEs occurring during the pre-treatment period.
- Treatment-emergent AEs are defined as AEs that develop, worsen (according to the Investigator's opinion), or become serious during the on-treatment period.
- Post-treatment AEs are defined as AEs that are reported during the post-treatment period.

For participants with multiple occurrences of the same PT, the maximum grade will be used.

The primary focus of AE reporting will be on TEAEs. Pre-treatment and post-treatment AEs will be described separately.

#### Treatment-emergent adverse events:

An overall summary of TEAEs will be provided. The number and percentage of participants who experience any of the following will be provided:

- TEAEs.
- TEAEs of Grade  $\geq 3$
- Grade 5 TEAE (any TEAE with a fatal outcome during the on-treatment period)

- Serious TEAEs
- Serious treatment-related TEAEs
- TEAE leading to partial intervention discontinuation
- TEAE leading to full intervention discontinuation
- Treatment-related TEAEs
- Treatment-related TEAEs of Grade  $\geq 3$

Number and percentage of participants experiencing TEAEs by primary SOC and PT will be summarized by NCI-CTCAE v 5.0 grade (all grades and Grade  $\geq 3$ ). Missing grades, if any, will be included in the “all grades” category. Similar summaries will be prepared for treatment-related TEAEs, TEAEs leading to partial intervention discontinuation, TEAEs leading to full intervention discontinuation, TEAEs leading to dose modification, serious TEAEs, TEAEs with fatal outcome, AESIs, and AEs/SAEs occurring during the post-treatment period. In addition, the number (%) of participants with any Grade 5 AE (TEAE and post-treatment) will be summarized.

The following deaths summaries will be generated:

- Number and percentage of participants who died by study period (treatment-emergent period, post-treatment period) and reasons for death (disease progression, AE, or other reason).
- All TEAEs leading to death by primary SOC and PT showing number and percentage (%) of participants.

#### **9.4.3.6 Clinical laboratory evaluations**

Clinical laboratory values will be analyzed after conversion into standard international units. International units will be used in all listings and tables.

When relevant, for laboratory variables, descriptive statistics for results and changes from baseline will be provided for the last value and the worst value (minimum and/or maximum value depending on the parameter) during the on-treatment period.

Hematology and clinical chemistry results will be graded according to the NCI-CTCAE v 5.0, when applicable. Number and percentage of participants with laboratory abnormalities (all grades and by grade) using the worst grade during the treatment period will be provided.

When the NCI-CTCAE v 5.0 grading scale is not applicable, the number of participants with laboratory abnormality out-of-normal laboratory range value will be displayed.

For laboratory variables graded by NCI-CTCAE:

- The number (%) of participants with abnormal laboratory tests at baseline will be presented by grade.
- The number (%) of participants with abnormal laboratory tests during the treatment-emergent period will be summarized by grade. When appropriate, the number (%) of participants with abnormality of any grade and with Grade 3-4 abnormalities will be provided.

[figure not shown]

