- Hematology and clinical chemistry results will be graded according to the NCI-CTCAE V5.0, when applicable. Number and percentage of participants with laboratory abnormalities (all grades and by grade) using the worst grade during the on-treatment period will be provided for the exposed population.
- **Analysis of other secondary endpoints:**
  - Plasma concentrations of SAR444245 will be summarized with descriptive statistics by each cohort.

**Data Monitoring/Other committee: Yes** (see [Section 10.1.5](#) for details).

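### Laboratory abnormalities are counted by worst on-treatment grade with no worsening-from-baseline condition, so the incidence endpoint includes abnormalities already present at entry

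*Protocol*

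**What the plan says.** Table 2 of the master protocol (section 3) lists among the secondary safety endpoints "Incidence of TEAEs, SAEs, laboratory abnormalities according to National Cancer Institute Common Terminology Criteria for Adverse Events (NCI CTCAE) V 5.0". Two places say how laboratory abnormalities are counted.

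- Synopsis, statistical considerations: "Number and percentage of participants with laboratory abnormalities (all grades and by grade) using the worst grade during the on-treatment period".
- Section 9.4.3.6: "Number and percentage of participants with laboratory abnormalities (all grades and by grade) using the worst grade during the treatment period will be provided". For CTCAE-graded variables it adds "The number (%) of participants with abnormal laboratory tests during the treatment-emergent period will be summarized by grade".

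Section 9.4.1 defines the treatment-emergent period purely as a time window, from first IMP to 30 days after last IMP. For adverse events, section 9.4.3.5 sets a condition on the event itself: "Treatment-emergent AEs are defined as AEs that develop, worsen", or become serious, in that window.

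Section 9.4.3.6 also plans two outputs that involve baseline: "The number (%) of participants with abnormal laboratory tests at baseline will be presented by grade" and, when relevant, "descriptive statistics for results and changes from baseline will be provided for the last value and the worst value".

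**The concern.** The same term carries two meanings. For adverse events, treatment-emergent means new, worse or newly serious. For laboratory tests it means only that the sample was taken in the window. The laboratory figure is therefore a period prevalence, reported under an endpoint called incidence.

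The entry criteria admit some of the values counted. Section 5.2 allows hemoglobin from 9 g/dL (E 26) and platelets from 100 x 10^3/µL (E 25), and sets no lymphocyte limit. A participant with hemoglobin 9.5 g/dL at baseline and throughout treatment is counted as abnormal on treatment.

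The trial is uncontrolled, so no other arm shows how much abnormality would be present anyway. The participant's own baseline is the only internal comparator, and the counting rule does not use it. Lymphocytes deserve attention: section 8.2 singles out transient lymphopenia for monitoring, and no entry floor limits the grade a participant may bring in.

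**Working it through.** **1. Which analytes are affected.** The protocol does not reproduce the CTCAE limits for hematology. I take hemoglobin, platelets and lymphocytes to be graded on fixed limits, so an unchanged value keeps its grade. AST/ALT and bilirubin differ: Substudy 01, Table 5, footnotes c to e, gives Grades 2 to 4 as multiples of baseline when baseline is abnormal. AST/ALT Grade 2 then starts above 3.0 x baseline.

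- Entry at 2.5 x ULN (E 28): 3.0 x 2.5 = 7.5 x ULN before Grade 2.
- Entry at 5 x ULN (E 28, liver metastases): 3.0 x 5 = 15 x ULN before Grade 2.

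An unchanged admitted AST/ALT value is therefore not counted at Grade 2 or above.

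**2. Size of the excess.** There is no planned figure for this endpoint to reproduce. Let b be the proportion abnormal at baseline who stay abnormal, and i the rate of new abnormality among the rest. Both are assumptions; the documents give neither.

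- Reported as written: b + (1 - b) x i
- Newly abnormal only: (1 - b) x i
- Excess: b

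With about 40 participants per cohort (section 9.2) and i = 20%:

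| b | As written | Newly abnormal | Excess, of 40 |
|---|---|---|---|
| 10% | 28% | 18% | 4 |
| 30% | 44% | 14% | 12 |
| 50% | 60% | 10% | 20 |

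With i = 0 the reported figure is b itself.

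**3. What the two planned tables recover.** Suppose 12 of 40 are abnormal at baseline and 20 of 40 on treatment.

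- If every baseline abnormality persists, the newly abnormal number 20 - 12 = 8.
- Without that assumption it lies between max(0, 20 - 12) = 8 and min(20, 40 - 12) = 20.

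Even with persistence, the number whose grade worsened is not fixed. Take the 12 as Grade 1 at baseline, and 12 Grade 1 plus 8 Grade 2 on treatment. If 8 participants went from Grade 0 to 2 and nobody else moved, 8 worsened. If 8 went from Grade 1 to 2 and 8 others from Grade 0 to 1, then 8 + 8 = 16 worsened. Both cases give the same two tables.

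**4. A hemoglobin illustration with no drug effect.** All inputs are assumed: true mean 11.5, 12.0 or 12.5 g/dL, SD 1.5, visit-to-visit SD 0.4, entry value at least 9, eight on-treatment samples, Grade 2 or worse below 10 g/dL. Results from 400,000 simulated participants per mean, for Grade 2 or worse:

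| Mean, g/dL | Baseline | Worst on treatment | Difference | Worsened to Grade 2 or more |
|---|---|---|---|---|
| 11.5 | 12.0% | 22.9% | 10.9 | 11.7% |
| 12.0 | 7.4% | 15.0% | 7.6 | 8.2% |
| 12.5 | 4.2% | 9.0% | 4.8 | 5.2% |

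A repeat run agreed to within 0.1 point. Roughly half of the on-treatment figure was present at baseline. The other half comes from taking the worst of eight noisy values, and a worsened-from-baseline count still includes it.

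**The case against.** The strongest reply is that nothing is mislabelled. Section 9.4.3.6 promises abnormal tests within a defined window and sets a baseline count by grade beside it, so pre-existing abnormality is disclosed. Changes from baseline to the last and worst value are planned when relevant, and an unchanged hemoglobin would show zero change there. Under section 10.3.1, clinically significant laboratory worsening is an adverse event, so it reaches the TEAE tables, which already require worsening. Section 9.4 calls itself a summary, and table layout is normally left to the SAP. In the hemoglobin illustration, subtracting one planned table from the other comes within 0.4 to 0.8 points of the true worsened figure.

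Most of this stands, and it limits the point to a minor one. It does not remove it. The protocol states a counting rule for a named endpoint; it does not leave the rule open, and a SAP that follows it inherits the mismatch. Change-from-baseline statistics do not give a number of participants. The subtraction worked in the illustration because true hemoglobin was held stable; step 3 shows that the tables alone do not guarantee it.

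A reader might go further and infer that baseline abnormalities are passed off as effects of SAR444245, or that every analyte and grade is inflated. The documents do not support that. Baseline grades are tabulated, AST/ALT and bilirubin at Grade 2 and above are baseline-relative, and, on the assumed CTCAE limits, admitted hemoglobin and platelet values do not themselves reach Grade 3-4. Nor do the first-in-human lymphopenia rates in section 4.3 show the effect: those are TEAE rates, so their counterpart is the adverse event analysis.

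**Conclusion.** The point holds in limited form. For analytes graded on fixed limits, the on-treatment percentage exceeds new-onset incidence by the baseline prevalence of persisting abnormalities. The planned outputs show that prevalence in aggregate but do not count the participants who worsened. The size cannot be stated from the documents, because baseline prevalence is not given; the 4 to 20 participants of 40 shown above follow from assumed prevalences of 10% to 50%. Lymphopenia has not been quantified.

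The endpoint is secondary, descriptive and untested, and the visible text ties no decision rule to it. The primary ORR analysis is untouched. This is a minor matter and a free improvement.

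**What to change.** In section 9.4.3.6, with a matching line in the synopsis:

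1. Keep the planned counts by baseline grade and by worst on-treatment grade.
2. Define the incidence figure for CTCAE-graded laboratory variables as participants whose worst on-treatment grade exceeds their baseline grade, and state how a missing baseline is handled (for example, as Grade 0).
3. Add a baseline-by-worst-grade shift table per analyte and cohort.

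The data are already collected, so the cost is minor programming and a short text change. The new count will still pick up visit-to-visit variation (5% to 12% at Grade 2 or worse in the illustration, with no drug effect), so it should be read as worsening observed on treatment, not as drug effect.
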